 - (3). Participants with recurrent disease > 6 months after platinum-containing adjuvant, neoadjuvant or definitive chemoradiation therapy given for locally advanced disease, who also subsequently progressed during or after a platinum doublet-based regimen given to treat the recurrence, are eligible.
- d) Evaluable disease by computed tomography (CT) or magnetic resonance imaging (MRI); radiographic tumor assessment performed within 28 days of start of study treatment.
- e) Cohorts A, A1, and B: Participants must have tissue submitted for PD-L1 immunohistochemical (IHC) testing prior to the treatment assignment. If PD-L1 results are available from another BMS study, or a commercially available complementary diagnostic using an acceptable antibody (ie, 28-8, 22-C3, SP263), these results are acceptable. PD-L1 results obtained using antibody SP142 are not acceptable.
- i) Either a formalin-fixed, paraffin-embedded (FFPE) tissue block or unstained tumor tissue sections, with an associated pathology report, must be submitted for biomarker evaluation prior to treatment assignment. The tumor tissue sample may be fresh or archival if obtained within 12 months prior to enrollment (6 months for slides).
 - ii) Tissue must be a core needle biopsy, excisional or incisional biopsy. Fine needle biopsies or drainage of pleural effusions with cytopins are not considered adequate for biomarker review. Biopsies of bone lesions that do not have a soft tissue component or decalcified bone tumor samples are also not acceptable.
 - (1). Samples collected via other procedures, including, but not limited to, endobronchial ultrasound (EBUS) guided biopsy, transbronchial lung biopsy

(TBLB) may be approved by the BMS medical monitor (MM)/study director (SD) on a case by case basis.

iii) Sufficient tissue (10-15 unstained slides) must be available.

- f) Prior palliative radiotherapy to non-central nervous system (CNS) lesions must have been completed at least 2 weeks prior to the treatment assignment. Participants with symptomatic tumor lesions at baseline that may require palliative radiotherapy within 4 weeks of the treatment assignment are strongly encouraged to receive palliative radiotherapy prior to starting study therapy. Lesions which have received or are anticipated to receive palliative RT may not be designated as target or non-target lesions in the baseline tumor assessment.

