7.7.2.1 Palliative Radiotherapy (All Cohorts)

On study palliative radiotherapy is not allowed on target lesions used to assess disease response and designated as such in the eCRF. Non-target bone lesions not so designated and that do not include lung tissue in the planned radiation field may be treated with palliative radiotherapy at any time while participants remain on study treatment. In addition, palliative radiotherapy to a single metastatic site, other than bone, is permitted in participants who do not require immediate initiation of second line systemic anti-cancer therapy. Such radiotherapy to non-bone lesions must not be given within 2 weeks of initiation of study therapy and such lesions are not permitted to be designated as baseline target lesions in the eCRF. Details of palliative radiotherapy should be documented in the source records and CRF. Details in the source records should include: dates of treatment, anatomical site, dose administered and fractionation schedule, and AEs.

Participants requiring palliative radiotherapy to designated target lesions must be discontinued from study therapy. Participants requiring palliative radiotherapy should be carefully assessed for disease progression. Participants considered as having progressive disease are required to discontinue study therapy, unless eligible to continue treatment beyond progression per the guidance in [Section 8.1.2](#).

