1.4 Baseline Documentation Of ‘Target’ And ‘Non-Target’ Lesions

When more than one measurable lesion is present at baseline all lesions up to a maximum of five lesions total (and a maximum of two lesions per organ) representative of all involved organs should be identified as target lesions and will be recorded and measured at baseline (this means in instances where patients have only one or two organ sites involved a maximum of two and four lesions respectively will be recorded).

Note: A maximum of two lesions can be selected per organ system. For example, a maximum of two lung lesions can be selected (selected from one lung or one lesion from each). A maximum of two lymph nodes can be selected at baseline, as the lymphatic system is considered one organ.

Target lesions should be selected on the basis of their size (lesions with the longest diameter), be representative of all involved organs, but in addition should be those that lend themselves to reproducible repeated measurements. It may be the case that, on occasion, the largest lesion does not lend itself to reproducible measurement in which circumstance the next largest lesion which can be measured reproducibly should be selected.

A sum of the diameters (longest for non-nodal lesions, short axis for nodal lesions) for all target lesions will be calculated and reported as the baseline sum diameters. If lymph nodes are to be included in the sum, then as noted above, only the short axis is added into the sum. The baseline sum diameters will be used as reference to further characterize any objective tumor regression in the measurable dimension of the disease.

All other lesions (or sites of disease) including pathological lymph nodes should be identified as non-target lesions and should also be recorded at baseline. Measurements are not required and these lesions should be followed as ‘present’, ‘absent’, or in rare cases ‘unequivocal progression’ (more details to follow). In addition, it is possible to record multiple non-target lesions involving the same organ as a single item on the case record form (eg, ‘multiple enlarged pelvic lymph nodes’ or ‘multiple liver metastases’).

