2.2 Evaluation of Non-Target Lesions

This section provides the definitions of the criteria used to determine the tumor response for the group of non-target lesions. While some non-target lesions may actually be measurable, they need not be measured and instead should be assessed only qualitatively at the time points specified in the protocol.

- **Complete Response (CR):** Disappearance of all non-target lesions. All lymph nodes must be non-pathological in size (< 10mm short axis).
- **Non-CR/Non-PD:** Persistence of one or more non-target lesion(s)
- **Progressive Disease (PD):** Unequivocal progression of existing non-target lesions.

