2.2.1.1 When the patient also has measurable disease

In this setting, to achieve ‘unequivocal progression’ on the basis of the non-target disease, there must be an overall level of substantial worsening in non-target disease such that, even in presence of SD or PR in target disease, the overall tumor burden has increased sufficiently to merit discontinuation of therapy. A modest ‘increase’ in the size of one or more non-target lesions is usually not sufficient to qualify for unequivocal progression status. Pleural effusions, pericardial effusions and ascites will not be followed as target or non-target lesions and will not contribute to response or progression. The designation of overall progression solely on the basis of change in non-target disease in the face of SD or PR of target disease will therefore be extremely rare.

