2.3.2 Time Point Response

At each protocol specified time point, a response assessment occurs. Table 2.3.2-1 provides a summary of the overall response status calculation at each time point for patients who have measurable disease at baseline. When patients have non-measurable (therefore non-target) disease only, Table 2.3.2-2 is to be used.

| Target Lesions | Non-Target Lesions | New Lesions | Overall Response |
|-------------------|-----------------------------|-------------|------------------|
| CR | CR | No | CR |
| CR | Non-CR/non-PD | No | PR |
| CR | Not evaluated | No | PR |
| PR | Non-PD or not all evaluated | No | PR |
| SD | Non-PD or not all evaluated | No | SD |
| Not all evaluated | Non-PD | No | NE |
| PD | Any | Yes or No | PD |
| Any | PD | Yes or No | PD |
| Any | Any | Yes | PD |

CR = complete response, PR = partial response, SD = stable disease, PD = progressive disease and NE = inevaluable

| Table 2.3.2-2: Time Point Response: Patients with Non-target Disease Only | | |
|--|--------------------|----------------------------|
| Non-Target Lesions | New Lesions | Overall Response |
| CR | No | CR |
| Non-CR/non-PD | No | Non-CR/non-PD ^a |
| Not all evaluated | No | NE |
| Unequivocal PD | Yes or No | PD |
| Any | Yes | PD |
| CR = complete response, PD = progressive disease and NE = inevaluable | | |

^a Non-CR/non-PD is preferred over SD for non-target disease since SD is increasingly used as endpoint for assessment of efficacy in some trials so to assign this category when no lesions can be measured is not advised.

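### Criterion 2f keeps palliatively irradiated baseline lesions off both lesion lists while Appendix 6 lists them as non-target, so the same scans can give different responses

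*Combined protocol and SAP*

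**What the plan says.** Three places in the protocol deal with how such a lesion is listed.

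- **Section 6.1, criterion 2f.** A lesion already treated with palliative radiotherapy, or expected to be, "may not be designated as target or non-target lesions in the baseline tumor assessment".
- **Appendix 6, section 1.4.** Once target lesions have been chosen, "All other lesions (or sites of disease) including pathological lymph nodes should be identified as non-target lesions and should also be recorded at baseline". Irradiated lesions are not excepted.
- **Section 7.7.2.1.** For on-study radiotherapy to a single non-bone site, "such lesions are not permitted to be designated as baseline target lesions in the eCRF". Non-target status is not mentioned. The same section says "Non-target bone lesions not so designated and that do not include lung tissue in the planned radiation field may be treated with palliative radiotherapy", so it envisages some irradiated lesions being on the non-target list.

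Section 9.1 has the investigator assess response by RECIST 1.1 as given in Appendix 6. No section says whether 2f or Appendix 6 takes precedence.

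**The concern.** A site cannot follow both 2f and Appendix 6 section 1.4 for the same lesion, and overall response depends on which lesions are listed. Sites that read the text differently would therefore score identical scans differently. ORR, PFS and DOR are investigator-assessed secondary endpoints in Cohorts A, B and C, and exploratory in A1. Progression also bears on whether treatment continues (Section 8.1.2).

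The protocol itself helps to create the lesions in dispute. Criterion 2f encourages radiotherapy before study treatment for symptomatic lesions that may need it within 4 weeks.

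**Working it through.** The plan gives no figure to reproduce, so the check applies Appendix 6 under each listing rule.

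**1. What an unlisted lesion can do.** Non-target PD is "Unequivocal progression of existing non-target lesions" (Appendix 6, 2.2), so an unlisted lesion cannot trigger it. It is not in the target sum. It was present at baseline, where Section 9.1 asks for all known sites to be imaged, so it is not a new lesion. CR requires target and non-target lesions to disappear, so an unlisted lesion generally does not block it. Lymph nodes are a possible exception, because section 2.2 requires all nodes to be of non-pathological size.

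**2. Whether Appendix 6 contains an implied exception.** Where it means to keep findings off both lists it says so: "Pleural effusions, pericardial effusions and ascites will not be followed as target or non-target lesions" (2.2.1.1). It says nothing comparable about irradiated lesions.

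**3. Measurable disease (Table 2.3.2-1).** Inputs: target status T (CR, PR, SD, PD) and irradiated-lesion status R (gone, persisting, unequivocally progressing), giving 4 × 3 = 12 combinations. Assumptions: the irradiated lesion is the only non-target candidate, there are no new lesions, and an empty non-target list does not prevent CR. Under 2f the response depends on T alone; under Appendix 6 it depends on T and R. The rows that decide are "CR | Non-CR/non-PD | No | PR" and "Any | PD | Yes or No | PD".

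**4. Non-target-only disease (Table 2.3.2-2).** Inputs: status O of the other non-target lesions (3 levels) and R (3 levels), giving 3 × 3 = 9 combinations. Under 2f the response follows O; under Appendix 6 it follows the worse of O and R.

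The combinations that differ are:

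| Disease | Other lesions | Irradiated lesion | Under 2f | Under Appendix 6 |
|---|---|---|---|---|
| Measurable | Target CR | Persists | CR | PR |
| Measurable | Target CR | Progresses | CR | PD |
| Measurable | Target PR | Progresses | PR | PD |
| Measurable | Target SD | Progresses | SD | PD |
| Non-target only | CR | Persists | CR | Non-CR/non-PD |
| Non-target only | CR | Progresses | CR | PD |
| Non-target only | Non-CR/non-PD | Progresses | Non-CR/non-PD | PD |

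So 4 of 12 and 3 of 9 differ; the other 8 and 6 agree. All seven differences are more favourable under 2f. They are counts of combinations, not frequencies.

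**5. Effect on the endpoints (Section 10.3.1).**

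- CR versus PR changes the CR rate. It leaves ORR unchanged, because confirmed CR and PR both count.
- PD versus no PD changes PFS and, in responders, DOR. It changes ORR only if the PD comes before the response is confirmed.
- CR versus Non-CR/non-PD changes ORR, but only in non-target-only disease. Such disease is possible because criterion 2d asks for evaluable, not measurable, disease.
- PFS is censored at the last evaluable assessment before any palliative local therapy. The PFS effect therefore falls mainly on lesions irradiated before entry, or progressing before on-study radiotherapy. DOR is censored only for subsequent anti-cancer therapy.

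**The case against.** The best defence is that 2f is a trial-specific exception to a generic appendix. Parts of Appendix 6 do read as a template: section 2.2.1.2 speaks of what happens in some trials, and section 2.3.1 defers to the nature of the study. That is a plausible intention, but the protocol never states it. It would also leave open how growth or persistence of an unlisted lesion is to be counted.

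Section 7.7.2.1 is also not clearly a third, conflicting rule. Barring target status is compatible with 2f's wider bar, and its non-target bone lesions may be ones whose radiotherapy was not foreseen at baseline. That stands: the direct conflict is between 2f and Appendix 6 section 1.4.

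A reader might infer that any growth in an irradiated lesion is PD under Appendix 6. It is not. With measurable disease, section 2.2.1.1 says a modest increase usually does not suffice and expects overall progression on non-target disease alone to be extremely rare. With only non-measurable disease, section 2.2.1.2 still asks for a substantial increase, comparable to 73% in volume.

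Finally, listing irradiated lesions could let shrinkage from radiotherapy count as response to study drug. That holds only where every baseline lesion was irradiated. Otherwise, listing the lesion adds a condition for CR and a route to PD, and cannot improve the response. The exception needs its own safeguard, given in the fix.

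**Conclusion.** The conflict is real and should be resolved, but its reach is limited. Followed as written, 2f can miss unequivocal progression and can record a CR while an irradiated lesion persists. The endpoints exposed are PFS, DOR and the CR rate. ORR is exposed only where PD precedes confirmation or disease is non-target-only. Three things limit the effect: progression on non-target disease alone is rare with measurable disease, PFS is already censored at on-study palliative local therapy, and the primary endpoint is safety with no formal hypothesis (Section 3.1.1).

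No headcount follows from the protocol. If one assumed that 10–20% of participants had such a lesion, that would be 0.10 × 400 = 40 to 0.20 × 400 = 80 in each of Cohorts A and B, and 10 to 20 of 100 in Cohort C. A reader might take these as numbers misclassified. They would be participants whose baseline recording is ambiguous, on an assumed rate; the number whose response status changes cannot be derived.

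Nor do the documents establish that a participant whose only lesion was irradiated satisfies criterion 2d, since evaluable disease is not defined there.

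**What to change.** State one listing rule in criterion 2f, Section 7.7.2.1 and Appendix 6 section 1.4. The preferred wording deletes *or non-target* from 2f, so that these lesions are never target but are recorded and followed as non-target. This keeps radiotherapy shrinkage out of the target sum and leaves progression detectable. If the sponsor prefers to keep 2f's full bar, Appendix 6 needs an explicit exception and a rule for how persistence and growth of the unlisted lesion count.

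Also require at least one non-irradiated, recordable baseline lesion for response evaluation, so that radiotherapy shrinkage alone cannot count as a response.

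For participants already enrolled, do not add lesions retrospectively. The trial is open-label and investigator-assessed, outcomes may be known, and follow-up scans would have to be re-read. Instead, flag participants with irradiated baseline lesions and report ORR, PFS and DOR with and without them as a sensitivity analysis.

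The cost is a short amendment, the work of identifying affected participants, and a little more analysis. No new scans are needed. The downside is slightly fewer CRs and slightly earlier progression events.

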6.1.1 Inclusion Criteria for Cohort A1 Special Population

4) Participants may be included in the 1L NSCLC special population cohort of the study with one of the following criteria. All other inclusion and exclusion criteria apply.

- a) ECOG PS 0 and 1 participants with untreated, asymptomatic brain metastases
 - i) Participants with untreated brain metastases must not require corticosteroids or anticonvulsant therapy.
- b) ECOG PS 0 and 1 participants with hepatic impairment, defined as follows:
 - i) Total bilirubin = 1.5-3.0 x ULN, and/or;
 - ii) AST/ALT = 3-5 x ULN
- c) ECOG PS 0 and 1 participants with renal impairment, defined as follows:
 - i) Creatinine clearance 20-39 mL/min (Cockcroft-Gault formula)
- d) ECOG PS 0 and 1 participants with HIV
 - i) Participants who are HIV positive must meet the following criteria:
 - (1). Acute or Chronic HIV infection. HIV-1 infection as documented by HIV rapid test performed in conjunction with screening (or ELISA, test kit, and confirmed by Western blot or other approved test). HIV plasma HIV-1 RNA below detected limit (limit of detection: 75) within 4 weeks prior to registration, without confirmed viral breakthrough for at least 6 months.
 - (2). HIV plasma HIV-1 RNA below detected limit (limit of detection: 75) within 4 weeks prior to registration, without confirmed viral breakthrough for at least 6 months.
 - (3). Participants with Chronic HIV must be asymptomatic/clinically latent, with CD4+ count of > 200 cells/mm³ obtained within 2 weeks prior to enrollment.
 - (4). Participants with a diagnosis of AIDS are excluded.
- e) Participants with ECOG PS 2 who, in the opinion of the investigator, are expected to be able to tolerate study treatment.

6.2 Exclusion Criteria

1) Target Disease Exceptions

- a) Participants with known EGFR mutations which are sensitive to available targeted inhibitor therapy (including, but not limited to, deletions in exon 19 and exon 21 [L858R] substitution mutations) are excluded. All participants with non-squamous histology must have been tested for EGFR mutation status, with the exception of participants with known KRAS mutations. Use of an FDA-approved EGFR test is strongly encouraged. Participants with non-squamous histology and unknown or indeterminate EGFR status are excluded.
- b) Participants with known ALK translocations which are sensitive to available targeted inhibitor therapy are excluded. If tested, use of an FDA-approved test is strongly encouraged. Participants with unknown or indeterminate ALK status may be enrolled.

2) Medical Conditions

- a) Participants with untreated CNS metastases are excluded.
 - i) Participants are eligible if CNS metastases are adequately treated and participants are neurologically returned to baseline (except for residual signs or symptoms related to the CNS treatment) for at least 2 weeks prior to treatment assignment. In addition, participants must be either off corticosteroids, or on a stable or decreasing dose of ≤ 10 mg daily prednisone (or equivalent) for at least 2 weeks prior to treatment assignment.
- b) Participants with carcinomatous meningitis.
- c) Participants must have recovered from the effects of major surgery or significant traumatic injury at least 14 days before treatment assignment.
- d) Active malignancy requiring concurrent intervention.
- e) Participants with an active, known or suspected autoimmune disease. Participants with type I diabetes mellitus, hypothyroidism only requiring hormone replacement, skin disorders (such as vitiligo, psoriasis, or alopecia) not requiring systemic treatment, or conditions not expected to recur in the absence of an external trigger are permitted to enroll.
- f) Participants with a condition requiring systemic treatment with either corticosteroids (> 10 mg daily prednisone equivalent) or other immunosuppressive medications within 14 days of treatment assignment. Inhaled or topical steroids, and adrenal replacement steroid > 10 mg daily prednisone equivalent, are permitted in the absence of active autoimmune disease.
- g) Participants with interstitial lung disease that is symptomatic or may interfere with the detection or management of suspected drug-related pulmonary toxicity.
- h) Known history of testing positive for human immunodeficiency virus (HIV) or known acquired immunodeficiency syndrome (AIDS)-with the exceptions noted for Cohort A1 participants. See [Appendix 9](#)
- i) Known medical condition that, in the investigator's opinion, would increase the risk associated with study participation or study drug administration or interfere with the interpretation of safety results.

3) Prior/Concomitant Therapy

- a) Prior treatment with an anti-PD-1, anti-PD-L1, anti-PD-L2, anti-CD137, or anti-CTLA-4 antibody, or any other antibody or drug specifically targeting T-cell co-stimulation or checkpoint pathways
- b) **Not applicable per Revised Protocol 04:** *Cohort B: Prior participation in a BMS study where participants were treated with nivolumab and/or ipilimumab, except when approved by Medical Monitor/Study Director*
- c) Treatment with botanical preparations (eg herbal supplements or traditional Chinese medicines) intended for general health support or to treat the disease under study within 2 weeks prior to randomization/treatment. Use of marijuana and its derivatives for treatment of symptoms related to cancer or cancer treatment are permitted if obtained by medical prescription or if its use (even without a medical prescription) has been legalized locally

4) Physical and Laboratory Test Findings for Cohorts A, B, and C

Please see [Section 6.1.1](#) Inclusion Criteria for Cohort A1 Special Population for physical and laboratory test findings

- a) White blood cells (WBC) < 2000/ μ L
- b) Neutrophils < 1500/ μ L
- c) Platelets < 100×10^3 / μ L
- d) Hemoglobin < 9.0 g/dL
- e) Serum creatinine > 1.5 x ULN, unless creatinine clearance \geq 40 mL/min (measured or calculated using the Cockcroft-Gault formula)
- f) Aspartate aminotransferase (AST)/ alanine aminotransferase (ALT): > 3.0 x ULN
- g) Total bilirubin > 1.5 x ULN (except participants with Gilbert Syndrome who must have a total bilirubin level of < 3.0x ULN)
- h) Any positive test for hepatitis B virus or hepatitis C virus indicating acute or chronic infection.

5) Allergies and Adverse Drug Reaction

- a) History of allergy or hypersensitivity to study drug components.

6) Other Exclusion Criteria

- a) Prisoners or participants who are involuntarily incarcerated. (Note: under certain specific circumstances a person who has been imprisoned may be included or permitted to continue as a participant. Strict conditions apply and Bristol-Myers Squibb approval is required.
- b) Participants who are compulsorily detained for treatment of either a psychiatric or physical (eg, infectious disease) illness

Eligibility criteria for this study have been carefully considered to ensure the safety of the study participants and that the results of the study can be used. It is imperative that participants fully meet all eligibility criteria.

